#### **5. What is your plan for secondary variable analysis?**

Secondary outcome variables (30-min measurements of P; 2-h measurements of P, FSH, E, T; LH pulse amplitude) will be analyzed via hierarchical mixed-effect ANOVA models (models/procedures identical to those above).

#### **6. Have you been working with a statistician in designing this protocol? Yes**

**IF YES, what is their name?** [name] (Department of Public Health Sciences)

#### **7. Will data from multiple sites be combined during analysis? No**

## **Biomedical Research**

#### **1. What will be done in this protocol?**

Interventions in this research study are not expected to directly benefit the volunteers, and all interventions (e.g., collection of blood, data, administration of estradiol and progesterone) are being done solely to answer a research question and generate generalizable knowledge.

Studies under this protocol will be performed in normally cycling women and in women with PCOS from 18 to 35 years old. Criteria for PCOS will be (a) clinical and/or biochemical evidence of hyperandrogenism, (b) oligomenorrhea, and (b) the absence of clinical or biochemical evidence of other potential causes of hyperandrogenism and/or oligomenorrhea. After informed consent is obtained, all potential subjects will undergo a screening history and physical exam. Subjects will need to fast for a minimum of 8 hours prior to screening blood draw. After informed consent is obtained, blood tests (~ 16 cc) will be drawn at 0800-0900 h as follows: LH, FSH, progesterone (P), estradiol (E2), total testosterone, SHBG, 17-OHP, androstenedione, DHEA-S, beta-hCG, TSH, prolactin, CBC, chemistry and liver panels, hemoglobin A1c, fasting insulin, and fasting glucose. Additionally, BOD POD® will be used to measure total fat mass, fat free mass, and percent body fat. Waist and hip circumference will be measured. If a low hematocrit and low hemoglobin with a low or low-normal MCV (i.e., likely related to iron deficiency) is seen, we will offer 1 month of iron treatment (ferrous gluconate 325 mg bid) with a subsequent recheck of hematocrit and/or hemoglobin. If hematocrit and/or hemoglobin are still low, we will offer 1 more month of iron treatment (ferrous gluconate 325 mg bid) with a subsequent recheck of hematocrit and hemoglobin. Only volunteers with a hematocrit  $\geq 36\%$  or a hemoglobin level  $\geq 12$  g/dl (after a maximum of 2 sequential months of iron treatment) will be allowed to proceed with frequent blood sampling (see below). Women with anemia will be treated with iron for a maximum of 2 sequential months before the 1st admission and/or before the 2nd admission. If they remain anemic after 2 sequential months of ferrous gluconate (325 mg bid), they will then be excluded from participation in the study.

IRB-HSR# 13368: Determining the rapidity with which exogenous P suppresses daytime LH (GnRH) pulse frequency in women during the follicular phase of the menstrual cycle (CRM001)

If three months have elapsed between (a) the subject's most recent safety labs and (b) an overnight admission, a CBC, chemistry and liver panel will be obtained prior to the overnight admission (or on admission) to exclude anemia and any other exclusion criteria.

This study follows a crossover design, with assessment of the acute effects of P and placebo (individually) on GnRH pulse frequency; subjects will be randomized to receive either P or placebo during the first overnight admission, with subsequent overnight study occurring during a subsequent cycle.

Women will begin E2 patches (0.1 mg/d per patch, 2 patches [delivering a total of 0.2 mg/d] placed on the abdomen and changed every 2 d) on the evening of day 4-8 of the study cycle (controls) or  $\geq 4$  days post-menses (PCOS). These patches will be continued for a total of 4 d, with overnight admission occurring on day 3 of E2 administration. Exogenous E2 administration will standardize hypothalamic exposure to E2 and help ensure the presence of sufficient hypothalamic P receptors.

Four to 5 days before a scheduled overnight admission, subjects will come to the CRU or alternate UVA clinical unit for an outpatient blood draw for P and beta-HCG (2 cc). If 30 days will have elapsed between (a) the most recent hemoglobin and hematocrit and (b) the scheduled overnight admission, a hemoglobin and hematocrit will also be drawn at this time (1cc). Note: A hematocrit  $\geq 36\%$  or hemoglobin  $\geq 12$  g/dl in the month before overnight admission is required to participate in the scheduled inpatient (frequent sampling) protocol.

After 3 d of E2 administration, women will undergo a 24-h sampling study in the CRU, alternate UVA hospital unit, or off-site hotel. Estradiol administration (E2 patches) will continue throughout the overnight admission. Subjects will be admitted to the CRU, alternate UVA hospital unit, or hotel at 1800 h (2 h prior to sampling). Beginning at 2000 h, blood will be obtained through an indwelling i.v. forearm heparin lock over a 24-h period as follows: LH every 10 min (1 ml); P every 30 min (1 ml); FSH, E2, and T every 2 h (assays to be run in same samples as LH and P). SHBG, fasting insulin, and fasting glucose (i.e., fasting since 2200 h) will be run on the 0600 h sample (extra 2 cc drawn). (Subjects will fast from 2200 to 0600 h.) After 10 h of sampling (i.e., at 0600 h), either oral micronized P (100 mg p.o.) suspension or placebo suspension will be administered (according to randomization). (NOTE: the study coordinator will pick up the P/placebo from the research pharmacy to send to the CRU, alternate UVA hospital unit, or hotel the evening before administration.) With exogenous P, we aim to achieve mean plasma P concentrations 4-8 ng/ml. Subjects will not be allowed to sleep during the day (i.e., from 0600 to 2200 h). Subjects will be encouraged to sleep from 2200 to 0600. When possible, sleep will be formally evaluated (extraoculograms, electroencephalograms, wrist actigraphy, etc.)footnote  
. At the completion of sampling, E2 patches will be discontinued. Volunteers will be discharged on oral iron (325 mg BID). We will ask women to eat only the food provided by the CRU staff.

Subjects will undergo another overnight study identical to the first (including pretreatment with E2, outpatient blood draw 4-5 days before admission, etc.), except that oral P will be exchanged for placebo or *vice versa* in accordance with the crossover design. (Subjects will again begin E2 patches on the evening of cycle day 4-8 [controls] or  $\geq 4$  days post-menses [PCOS].) In this way, we will be able to standardize any change in GnRH pulse frequency after P administration to any change in GnRH pulse frequency after placebo administration.

If the subject does not have hematocrit  $\geq 36\%$  or hemoglobin  $\geq 12$  g/dl shortly before the second scheduled overnight admission, we will offer 1 month of iron treatment (ferrous gluconate 325 mg bid) with a subsequent recheck of hematocrit and/or hemoglobin. If hematocrit and/or hemoglobin are still low, we will offer 1 more month of iron treatment (ferrous gluconate 325 mg bid) with a subsequent recheck of hematocrit and/or hemoglobin. Only volunteers with hematocrit  $\geq 36\%$  or hemoglobin level  $\geq 12$  g/dl (after a maximum of 2 sequential months of iron treatment) will be

---

 Update at time of 5-year renewal April 2017: With regard to the formal sleep evaluation, we have had difficulties obtaining formal polysomnography because of scheduling difficulties with a sleep technician, primarily related to (a) limited availability of sleep technicians for CRU studies and/or (b) increased competition for sleep technicians. For this reason, we have been unable to perform formal sleep studies for the past several years. However, we will routinely perform wrist actigraphy. We will use the Motionlogger Basic-L wrist actigraphy unit (Ambulatory Monitoring, Inc.), which is a watch-like device that contains an accelerometer. This device captures subject movement data, which allows estimation of sleep periods. This watch-like device will be worn on the wrist by the research participant during the CRU admission. There are no known risks associated with wrist actigraphy.

allowed to proceed with the second overnight admission. If three months have elapsed between (a) the subject's most recent safety labs and (b) the second overnight admission, a CBC, chemistry and liver panel will be obtained prior to the overnight admission (or on admission) to exclude anemia and any other exclusion criteria.

The study will end after the second overnight admission. Subjects will be asked to continue oral iron supplementation for at least 30 d after this last overnight admission.

ADDITIONAL NOTE: As this is a study to determine the effects of acute progesterone administration on LH hormone regulation, it is important to study subjects during the follicular phase (a time when progesterone should be low, < 1.0), rather than during the luteal phase (when progesterone is high). For ovulatory control subjects, the timing of the luteal phase is predictable, so admission usually occurs around menstrual cycle day 7-11 (during the follicular phase). However, subjects with polycystic ovary syndrome have infrequent/irregular ovulation and infrequent/irregular luteal phases, so it is harder to predict when they will be in the luteal phase. For this reason, overnight admission is scheduled at a time that is  $\geq 7$  days since their last menses began; and a progesterone level is checked within 1-5 days before the overnight admission, to help rule out the possibility that women will be studied during the luteal phase (i.e., when progesterone levels are high). Following completion of the second overnight admission, samples will be assayed in the Center for Research in Reproduction Ligand Assay Core Lab for progesterone and LH. If it is found that a subject had a high progesterone level (> 1.0 ng/mL) prior to administration of progesterone/placebo syrup at 6am during either of their study admissions, the subject will be asked to repeat that particular study admission at a time when they are in the follicular phase of their cycle (progesterone < 1.0 ng/mL). The subject would be asked to wait the appropriate 8 weeks before scheduling the repeat study admission, so as not to put the subject at undue risk for anemia. The exact timing of the repeat study admission will depend on the subject's menstrual cycle. We would obtain all of the appropriate safety labs prior to studying the subject for a final study admission (to ensure subject safety). And to prevent a repeat occurrence of catching the subject in the wrong phase of her cycle, a progesterone would be checked one to two days before admission. Importantly, in such a situation, subjects would not be obligated to repeat the study admission, and they would receive \$300 for completing the study even if they do not repeat the admission. However, if they indeed complete the extra admission, we would offer additional compensation of \$100 for completion of this extra study admission, consistent with compensation for each overnight admission under this protocol.

**2. List the procedures, in bullet form, that will be done for RESEARCH PURPOSES as stipulated in this protocol.** ALL

**3. Do you confirm that, except for blood draws through a peripheral site, that all invasive procedures will be performed by a licensed health care provider under the supervision of an MD?**

NA, this study only involved blood draws by a licensed health care provider within the UVA hospital system.

**4. Will you be using data/specimens in this study that were collected previously, with the use of a research consent form, from another research study?** No

**5. Will any of the procedures listed in item # 2 have the potential to identify an incidental finding? This includes ALL procedures, assessments and evaluations that are being done for RESEARCH PURPOSES that may or may not be considered investigational.** Yes

▶ IF YES, check one of the following two options:

**X** The examination(s) utilize(s) the same techniques, equipment, etc., that would be used if the subject were to have the examination(s) performed for clinical care. **There exists the potential for the discovery of clinically significant incidental findings.**

- The PI takes full responsibility for the identification of incidental findings:

IRB-HSR# 13368: Determining the rapidity with which exogenous P suppresses daytime LH (GnRH) pulse frequency in women during the follicular phase of the menstrual cycle (CRM001)

- The PI will inform the subjects verbally of all incidental findings that are of clinical significance or are of questionable significance.
- A follow-up letter describing the finding should be provided to the subject with instructions to either show the letter to their PC or if the subject has no PCP, the subject should be instructed to make an appointment at UVa or at the Free Clinic.

**6. Do any of the procedures listed above, under question # 2, utilize any imaging procedures for RESEARCH PURPOSES? No**

**7. Will you be using viable embryos? No**

**8. Will you be using embryonic stem cells? No**

**9. If this protocol involves study treatment, explain how a subject will be transitioned from study treatment when they have completed their participation in the study. NA**

**10. Will your study involve measures used to screen or assess for depression and/or suicidality for research purposes? No**

**11. Where will the study procedures be done?**

UVa , but not medical center facilities: Clinical Research Unit (Barringer)

**12. If the study involves medical risk and study procedures will be done outside of the UVa Medical Center what is your plan to protect the subjects in case of a medical emergency?**

MD, RN, onsite during procedures

Individual trained in CPR on site during procedures

AED and Individual trained to use it onsite

Call 911

Other : Call Study staff

**13. Are any aspects of the study kept secret from the participants? No**

**14. Is any deception used in the study? No**

## Family History/Pedigree

**1. What kind of information is being sought?**

Family history (no questionnaire is being used).

**2. What identifiers will be recorded with any of the following info (e.g. names, initials, relationship such as mother, father, brother, sister, random number)? Relationship status.**

**3. Will HIPAA identifiers will recorded? No**

4. Does any of the information sought potentially expose the subject or a family member to additional risk?  
No

## Specimens

### Specimen Information

1. Describe the type of specimen to be used: Blood

2. Will the specimen be obtained BEFORE a subject has signed a consent form? No

3. Will you be using discarded specimens? No

▶ IF NO, where will blood be drawn?

in the clinical research unit (CRU)

▶ IF NO, who will draw the blood?

a member of the study team who is an individual licensed to practice medicine or osteopathy, a nurse practitioner, or a physician assistant employed by UVa School of Medicine

▶ IF NO, and taking a blood sample, will blood be taken more than 2 times/week? Yes

▶ IF NO, and taking a blood sample, check the option(s) below which match the subject population.

healthy, non-pregnant adults who weigh at least 110 pounds.

Amount will NOT exceed 550 cc in an 8 week period

Amount to exceed 550 cc in an 8 week period

▶ IF NO, will blood ONLY be obtained via a peripheral blood stick? Yes

### Specimen Labeling

1. What information/ HIPAA identifiers will be on the specimen label when it is given to the study team (from clinical labs or other source outside the study team) and/or what information will you put on the specimen?

Name, medical record #, CRR protocol #, date of birth, time (date and clock hour) drawn

2. If the specimen is given to the study team with information on the label will you delete any of the information on the specimen label? No

3. Will any additional data be linked to the specimen by way of a code? No

4. Will the analysis on the specimen be done soon (within 24 hours) after it is collected?

Yes and No. See the explanation below.

Samples from the screening exam that are analyzed by UVA clinical labs will generally be run within 24 hrs.

► **IF NO, where will the specimen be stored until analysis is done?**

Some samples from the screening exam (e.g., TSH, LH, FSH, P, Testosterone, E2 and insulin) and all samples from the inpatient admissions will be analyzed and stored in the UVA Center for Research in Reproduction Ligand Core lab Suhling Building, Rooms 6918 & 6921, IBC #132-02.

**Specimen Shipping**

1. **Do you plan to ship any specimens outside of UVA?**No

**Specimen Security**

The following security precautions will be implemented:

- Specimens will be kept in a locked freezer/ or locked room
- Specimens will be stored with HIPAA identifiers. Access to the freezer/room will be limited to authorized personnel. Specimens with HIPAA identifiers will never be shared outside of UVA without the written permission of the subject.

**Data and Safety Monitoring Plan**

1. **Definition:**

1.1 **How will you define adverse events (AE) for this study?**

An adverse event will be considered any undesirable sign, symptom or medical or psychological condition **even if the event is not considered to be related** to the investigational drug/device/intervention. Medical condition/diseases present before starting the investigational drug/intervention will be considered adverse events only if they worsen after starting study treatment/intervention. An adverse event is also any undesirable and unintended effect of research occurring in human subjects as a result of the collection of identifiable private information under the research. Adverse events also include any problems associated with the use of an investigational device that adversely affects the rights, safety or welfare of subject s.

1.2 **How will you define serious adverse events?**

A serious adverse event will be considered any undesirable sign, symptom, or medical condition which is fatal, is life-threatening, requires or prolongs inpatient hospitalization, results in persistent or significant disability/incapacity, constitutes a congenital anomaly or birth defect, is medically significant and which the investigator regards as serious based on appropriate medical judgment. An important medical event is any AE that may not result in death, be life-threatening, or require hospitalization but may be considered an SAE when, based upon appropriate medical judgment, it may jeopardize the patient and may require medical or surgical intervention to prevent one of the outcomes listed in the definitions of SAEs.

1.3 **What is the definition of an unanticipated problem?**

Do not change this answer

An unanticipated problem is any event, experience that meets ALL 3 criteria below:

- Is unexpected in terms of nature, severity or frequency given the research procedures that are described in the protocol-related documents AND in the characteristics of the subject population being studied
- Related or possibly related to participation in research. This means that there is a reasonable possibility that the incident may have been caused by the procedures involved in the research study.
- The incident suggests that the research placed the subject or others at greater risk of harm than was previously known or recognized OR results in actual harm to the subject or others

#### 1.4 What are the definitions of a protocol violation and/or noncompliance?

Do not change this answer

A **protocol violation** is defined as any change, deviation, or departure from the study design or procedures of research project that is NOT approved by the IRB-HSR prior to its initiation or implementation. Protocol violations may be major or minor violations.

**Noncompliance** can be a protocol violation OR deviation from standard operating procedures, Good Clinical Practices (GCPs), federal, state or local regulations. Noncompliance may be serious or continuing.

Additional Information: see the IRB-HSR website at

[http://www.virginia.edu/vpr/irb/HSR\\_docs/Forms/Protocol\\_Violations\\_%20Enrollment\\_Exceptions\\_Instructions.doc](http://www.virginia.edu/vpr/irb/HSR_docs/Forms/Protocol_Violations_%20Enrollment_Exceptions_Instructions.doc)

#### 1.5 If pregnancy occurs how will this information be managed?

Unanticipated Problems- will follow Unanticipated Problem recording and reporting procedures outlined in section 3. Note that pregnancy could not be deemed to be related/possibly related to this study, as none of the procedures increases likelihood of pregnancy, and subjects are specifically required to avoid pregnancy.

#### 1.6 What is the definition of a Protocol Enrollment Exception?

NA- No outside sponsor

#### 1.7 What is the definition of a data breach?

Do not change this answer

A data breach is defined in the HITECH Act (43 USC 17932) as an unauthorized acquisition, access, or use of protected health information (PHI) that compromises the security or privacy of such information.

Additional Information may be found on the IRB-HSR Website: [Data Breach](#)

## 2. Identified risks and plans to minimize risk

### 2.1 What risks are expected due to the intervention in this protocol?

Expected Risks related to study participation.	Frequency
Risks associated with venipuncture	
Discomfort	 Occurs frequently  Occurs infrequently  Occurs rarely  Frequency unknown
Bruising	 Occurs frequently  Occurs infrequently  Occurs rarely  Frequency unknown
Infection	 Occurs frequently  Occurs infrequently  Occurs rarely  Frequency unknown, but likely to be very rare
Blood clot at the site of intravenous catheter insertion	 Occurs frequently  Occurs infrequently  Occurs rarely  Frequency unknown
Risks of frequent blood draw	
Anemia	 Occurs frequently  Occurs infrequently  Occurs rarely  Frequency unknown
Risk to Fetus	Unknown risk to fetus
Risk of Progesterone	
Fluid retention	May occur with longer-term P administration, but this would not be expected after one dose of P.
Sleepiness	 Occurs frequently  Occurs infrequently  Occurs rarely  Frequency unknown
Mood swings	Occurs with longer-term P administration, but rare after one dose of P.
Mild vaginal bleeding	Generally occurs shortly after discontinuation of a one-week course of exogenous P and E2. We do not expect the same to occur after only one dose of P.
Risk of Estradiol	
Local skin irritation at the site of E2 patch application	May occur in approximately 15-20% of subjects
Deep Vein Thrombosis	 Occurs frequently

	 Occurs infrequently  Occurs rarely  Frequency unknown, however occurs very rarely with long-term estrogen use (as with oral contraceptive pills), so would expect to be exceedingly rare with the short term administration in this protocol.
Mild nausea	 Occurs frequently  Occurs infrequently  Occurs rarely  Frequency unknown
Swelling or breast tenderness	 Occurs frequently  Occurs infrequently  Occurs rarely  Frequency unknown
Hot flashes	 Occurs frequently  Occurs infrequently  Occurs rarely  Frequency unknown
Risk of Iron Supplementation	
nausea	 Occurs frequently  Occurs infrequently  Occurs rarely  Frequency unknown
constipation	 Occurs frequently  Occurs infrequently  Occurs rarely  Frequency unknown
dark or black stools	 Occurs frequently  Occurs infrequently  Occurs rarely  Frequency unknown
Risk for early termination of study participation if subject becomes pregnant	Subjects are not expected to have decreased infertility as a result of study medications (i.e., this short course of physiologic E2 and P will not provide contraception). Therefore, sexually active subjects may get pregnant during this protocol. If the volunteer becomes pregnant, the study and all study medications will be discontinued.
Reproductive Risks Specify potential reproductive risks	Minimized due to the requirements of this protocol.
Violation of subject's privacy and confidentiality	Minimized due to the requirements of the privacy plan in this protocol

**2.2 List by bullet format a summary of safety tests/procedures/observations to be performed that will minimize risks to participants:**

- Risks of venipuncture will be minimized by using proper sterile technique
- Risk of anemia will be reduced in the following manner: A hemoglobin and hematocrit will be obtained and reviewed prior to each CRU sampling study, and only volunteers with a hematocrit  $\geq 36\%$  or a hemoglobin  $\geq 12$  will be allowed to proceed with the frequent sampling study. The one exception to this rule is that those subjects documented to have a hematocrit  $\geq 36\%$  or Hemoglobin  $\geq 12$  g/dl in the month before overnight admission will not be required to have a repeat hematocrit and hemoglobin on overnight admission.
- Risk of fetal exposure to study drugs will be reduced by having a serum pregnancy test obtained and reviewed prior to each overnight sampling study. If the volunteer is pregnant, the study and all study medications will be discontinued.
- A history and physical will be performed at screening. Women with a history of any disorders that may potentially be complicated by long-term iron supplementation, such as hemochromatosis and polycythemia vera, will be excluded. Women with a significant history of cardiac or pulmonary dysfunction (e.g., known or suspected congestive heart failure; known or suspected coronary atherosclerosis; asthma requiring systemic intermittent corticosteroids; etc.) will be excluded. We will exclude women with a history of any disorders that may potentially be complicated by hormonal treatment, such as DVT and breast, ovarian, or endometrial cancer.
- Risk from use of estradiol patch will be reduced by instructing subjects to rotate sites of their E2 patch to avoid skin irritation and/or rash.
- Risk from iron supplementation will be reduced by instructing subjects to take their iron tablets with food and a full glass of water. They will be told to include whole grains and fruits and vegetables in their diet for fiber.
- A comprehensive metabolic panel will be performed at screening. Women with liver enzymes, alkaline phosphatase, or bilirubin  $> 1.5$  times upper limit of normal (confirmed on repeat) will be excluded, with the exception that mild bilirubin elevations will be accepted in the setting of known Gilbert's syndrome. Women with abnormal renal function (i.e., serum creatinine  $> 1.4$ ) will be excluded. Women with abnormal sodium, potassium, or bicarbonate concentrations  $< 20$  or  $> 30$  (confirmed on repeat) will be excluded.
- If three months have elapsed between (a) the subject's most recent safety labs and (b) an overnight admission, a CBC, chemistry and liver panel will be obtained prior to the overnight admission (or on admission) to exclude anemia and any other exclusion criteria.
- Subjects who are asked to repeat a study admission at a time when they are in the follicular phase of their cycle will be asked to wait the appropriate 8 weeks to schedule the repeat study admission so as not to put the subject at undue risk for anemia. All appropriate safety labs will be obtained prior to studying the subject for a final study admission to ensure subject safety.

- Subjects will have frequent (at least every 10 minutes) contact with CRU nursing personnel and will be asked to report any unusual symptoms occurring during the protocol.

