**To minimize the risk of having >500 ml of blood drawn within 48 hours:**

A hemoglobin level will be drawn within 30 days prior to the visit at which the blood will be drawn. The blood will not be drawn if the levels do not meet the criteria below:

- Hematocrit at least 36% and/or a hemoglobin level at least 12 g/dl

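### The 30-day haemoglobin/haematocrit waiver tests only the age of the value, so the second 24-hour bleed can be cleared on a value drawn before the first (minor safety correction)

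*Combined protocol and SAP*

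**What the plan says.** Three places in the protocol govern the haemoglobin/haematocrit check before a sampling admission.

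- **Biomedical Research, question 1.** An outpatient visit takes place 4-5 days before each admission. Progesterone and beta-hCG are always drawn there. Haemoglobin and haematocrit are drawn only on a condition: "If 30 days will have elapsed between (a) the most recent hemoglobin and hematocrit and (b) the scheduled overnight admission".
- **Data and Safety Monitoring Plan, section 2.2.** The general rule is a check before every sampling study. The single exception is for subjects with a qualifying value, who "in the month before overnight admission will not be required to have a repeat hematocrit and hemoglobin on overnight admission".
- **The paragraph on drawing more than 500 ml within 48 hours.** "A hemoglobin level will be drawn within 30 days prior to the visit at which the blood will be drawn".

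On spacing, the crossover is described only "with subsequent overnight study occurring during a subsequent cycle". The 8-week wait in the additional note to question 1, repeated in section 2.2, applies to an admission that has to be redone because progesterone was high. It does not apply to the ordinary interval between admissions 1 and 2.

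For the second admission, question 1 says that if a woman does not have a qualifying value "shortly before the second scheduled overnight admission, we will offer 1 month of iron treatment", followed by a recheck. How close to the admission that value must be is not defined.

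**The concern.** A haemoglobin value is useful before a bleed because it reflects the woman's state at that point. Once a 24-hour sampling study has intervened, a value from before it no longer does. All three statements of the rule would still accept it if it is recent enough.

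Anaemia is the one risk listed for frequent blood drawing, with frequency given as unknown (section 2.1), and participants have no direct benefit. The protocol also admits women who needed iron to reach the threshold, and they may start with little margin. If the recheck between the bleeds is skipped, nothing triggers the iron treatment and possible deferral that the protocol sets out for the second admission.

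This is a participant-safety point. It does not touch the sample size or the analysis.

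**Working it through.** **Check on the schedule.** Controls start oestradiol on cycle day 4-8 and are sampled after 3 days: 4 + 3 = 7 and 8 + 3 = 11. This reproduces the protocol's own statement that control admissions fall around day 7-11.

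**Blood volume** (question 1). Over 24 hours, LH at 1 ml every 10 min gives 144-145 ml and progesterone at 1 ml every 30 min gives 48-49 ml. The 0600 h sample adds 2 ml. FSH, oestradiol and testosterone use the same samples.

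- Per admission: 144 + 48 + 2 = 194 ml, to 145 + 49 + 2 = 196 ml.
- Whole study, with 16 cc at screening and two outpatient draws of 3 cc: 2 × 194 + 16 + 6 = 410 ml, to 2 × 196 + 16 + 6 = 414 ml.

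**Rule applied.** I assume a redraw is required once the value is 30 days old or more, and I read the month in section 2.2 as 30 days.

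**Women with PCOS.** Admission must be at least 7 "days since their last menses began; and a progesterone level is checked within 1-5 days before the overnight admission". There is a minimum cycle day but no maximum. Let menses begin D days after admission 1.

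- Earliest admission 2: D + 7 days after admission 1.
- Age at admission 2 of a value drawn at the visit 4-5 days before admission 1: D + 11 or D + 12 days.
- No redraw if D + 11 ≤ 29, so D ≤ 18; or D + 12 ≤ 29, so D ≤ 17.

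| D | Gap between admissions | Age of value at admission 2 |
|---|---|---|
| 10 | 17 days | 21-22 days |
| 14 | 21 days | 25-26 days |

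Question 1 also says oestradiol starts at least 4 days post-menses. If that runs from the end of bleeding, and bleeding is assumed to last 5 days, the gap becomes D + 5 + 4 + 3 = D + 12. The value is then D + 16 or D + 17 days old, so D must be at most 13 or 12.

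**Controls** (complete by April 2017, shown for scale). Assuming consecutive cycles, interval = cycle length + (start day 2 − start day 1). Start days 4-8 in each cycle give 25 pairs. The table counts pairs in which a value from before admission 1 is still under 30 days old at admission 2.

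| Assumed cycle length | Drawn 4 days before admission 1 | Drawn 5 days before |
|---|---|---|
| 26 days | 10 of 25 | 6 of 25 |
| 28 days | 3 of 25 | 1 of 25 |
| 30 days | 0 | 0 |

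If the value was drawn on the day of admission 1, the count at 28 days is 19 of 25. These are counts of date pairs, not probabilities.

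**Possible effect on haemoglobin.** Assume a blood volume of 3.5-5 L, a starting value of 12.0 g/dl, full restoration of volume and no red-cell recovery. The fall is 12 × 194/5000 = 0.47 g/dl to 12 × 196/3500 = 0.67 g/dl, leaving about 11.3-11.5 g/dl.

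**The case against.** The best reply is that a current result for admission 2 is plainly intended. Section 2.2 speaks of each sampling study, question 1 has its own provision for the period just before the second admission, and the second study is to be identical to the first, including the outpatient draw. The waiver could also be read as sparing women only a duplicate test on the day. That supports the intent, but no sentence requires a draw after the first bleed. At the outpatient visit, haemoglobin remains conditional on the 30-day trigger.

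Second, the D limits of 17-18 depend on haemoglobin having been drawn at the visit before admission 1, which is itself conditional. If the latest value was instead a days old at admission 1, the requirement is a + D + 7 ≤ 29, so D ≤ 22 − a: at most 7 for a = 15, at most 2 for a = 20, and none above 22. This stands, and it narrows the window.

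Third, the PCOS case needs a late-cycle first admission with low progesterone, menses soon afterwards, and prompt rebooking. These women are oligomenorrhoeic, so the sequence is possible rather than typical.

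Fourth, total blood of 410-414 ml is below the 550 cc per 8 weeks mentioned under Specimens, and iron is given at discharge. Because most statements of the threshold accept either haematocrit of at least 36% or haemoglobin of at least 12 g/dl, a haemoglobin below 12 would not by itself always bar admission. These points limit the severity but do not close the gap.

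**Conclusion.** The concern holds, as a minor one. Followed literally, the waiver allows a second bleed of about 195 ml to be cleared on a value taken before the first. No minimum interval or other rule prevents this; the three-month safety-lab rule is too long to help.

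For PCOS, the window is D up to 17-18 days, or 12-13 on the stricter timing reading with an assumed 5-day bleed. Both ranges are conditional on a haemoglobin draw 4-5 days before admission 1, and an older value shortens them. The documents do not give the timing of the next menses, so the frequency is unknown. The haemoglobin fall of about 0.5-0.7 g/dl rests on an assumed blood volume and ignores recovery and iron. Staff may already recheck in practice; the written rule does not make them.

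**What to change.** Add one sentence in each of the three places (Biomedical Research question 1, section 2.2, and the paragraph on more than 500 ml in 48 hours): a haemoglobin or haematocrit value drawn before an intervening sampling admission does not satisfy the 30-day allowance. Draw the new value at the outpatient visit already scheduled 4-5 days before admission 2. The thresholds, the 30-day window and the spacing of admissions can stay as they are.

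The cost is 1 cc more blood for some women, already counted in the 410-414 ml total. An occasional second admission would be put back by 1-2 months for iron, which is the protection the protocol already provides for.
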